Length of Covid-19 hospitalisation	Finland	National Care Register for Health Care and the National Infectious Diseases Register. Time between admission and final discharge date.	Categorical (adjustment variable	
	Norway	The Norwegian Intensive Care and Pandemic Registry (NIPaR). Time between admission and final discharge date.	for objective #3 only; 4 levels)e: ≤2 days, 3-5 days, 6-14 days, >14 days	
	Sweden	The Swedish Patient Register and the Register on surveillance of notifiable communicable diseases (SmiNet). Time between admission and final discharge date.		

<sup>a Due to data availability in Sweden, the country-specific end of study period might be some weeks earlier. For the bivalent 4 dose vs monovalent 4 dose comparisons, we will consider whether alternative time period bins should be used for these analyses to optimize the balance between covariate control and matched cohort size. b To account for the risk of severe Covid-19, we will adjust for targeted Covid-19 high-risk groups of severe Covid-19, specifically established for each country. In Denmark, the Covid-19 vaccine priority groups were governmentally assigned and individuals were prioritised according to the risk of severe infection (identified by the treating physicians) as well as whether being health or social care workers. In the remaining countries, the variable was constructed based on the identification of vulnerable individuals (as defined by those receiving nursing care or living in nursing homes) and whether being health or social care workers. c Autoimmunity-related conditions includes a range disorders such as inflammatory bowel diseases, diseases involving the blood, immune mechanism or endocrine systems, inflammatory rheumatic diseases, psoriasis, lupus erythematosus, multiple sclerosis; subject to country-specific definitions. The selected diagnosis codes to define comorbidities were country-specific, based on inputs from national experts and country-specific registration practices as part of the general national surveillance purposes. This was done as we anticipated that

country-specific definitions were likely better at identifying comorbidity-related risk groups within each country than a common set of code definitions.  $^{\rm d}$ The date defines the first day where omicron (sublineages BA.1 and BA.2) accounted for  $\geq$ 90% of all registered SARS-CoV-2 infection cases within the country as per national surveillance data of SARS-CoV-2 variants.  $^{\rm e}$ Upon examination of the data distribution, we will consider whether this variable should be included as a spline instead of categorical.

#### 9.4 Data sources

All data sources are nationwide registers in native format. All study subcontractors have access to their country-specific data and can link data between registers for the purpose of our study. Given the no-to-very-little lag time of the data source, our analyses will be reflecting real-time information. We will have full data availability for all variables (with no missing data; all the exposures, outcomes, or covariates are either present or not) during the study period and as reporting to national registers is mandatory/structurally implemented, this provides a near-complete follow-up of all residents over time.

Country/data source	Details
Denmark	
The Civil Registration System (14)	The register provides the unique personal identifier for all permanent residents of Denmark that allows linkage between all Danish health care registers and civil registrations systems. In addition, it holds general demographic information such as birthdate and sex as well as continuously updated information and dates on historical addresses, immigration and emigration status, and death.
The Danish Vaccination Register (15)	The register holds information on all vaccinations administered in Denmark including vaccination date, type/trade name, dose, and product batch number ever since Nov 15, 2015 (where reporting to the register became mandatory). Specifically related to this study, the Danish Health Agency have provided the governmentally assigned Covid-19 vaccine priority groups that were prioritised groups according to the risk of severe infection as well as whether being health and social care workers.
The Danish Microbiology Database (16)	Information on positive PCR tests for SARS-CoV-2 are obtainable via The Danish Microbiology Database (MiBa) that has data on all microbiology samples analysed at Danish microbiology departments as well as test results, date of sampling, date of analysis, type of test, and interpretation of test. The SARS-CoV-2 PCR tests are freely available to all individuals in Denmark regardless of symptoms status.
The National Patient Register (17)	The register holds information on all hospital contacts in Denmark including the duration of the contact, and diagnoses, which are assigned by the treating physician and registered according to ICD-10 classification system (since 1994).
Finland	
Finnish Population Information System (18)	The register is held by the Digital and Population Data Services Agency and contains personal data on all permanent residents in Finland such as the unique personal identifier, date of birth, place of residence, date of death, and date of immigration, and emigration.
Register of Social Assistance (19)	The register is held by the Finnish Institute for Health and Welfare and contains information on individuals receiving long-term care and/or social assistance (in e.g., nursing homes, people's own homes or other institutions) including social rehabilitation.

Country/data source	Details
Social and Healthcare Professionals Register (20)	The register holds data on individuals right to act as health care personnel.
National Vaccination Register (21)	The register is based on the Register of Primary Health Care Visits and contains information on all Covid-19 vaccinations administered in Finland including date of vaccination, batch number, and trade name.
National Infectious Diseases Register (22)	The register is held by the Finnish Institute for Health and Welfare and contains information on notifiable diseases in accordance with the Finnish Communicable Diseases Act that must be reported by the laboratories and the treating-physicians, or the physician performing an autopsy and hold information on sample dates of all laboratory-confirmed SARS-CoV-2 infections in Finland
National Care Register for Health Care (23)	The register is held by the Finnish Institute for Health and Welfare and comprises information on all inpatient and outpatient hospital contacts in Finland, including admission and discharge dates, whether hospitalisation was planned or acute, codes for discharge diagnoses (according to ICD-10) and surgical procedures, and whether discharged as deceased, to own private residence or other health care facilities.
Special Reimbursement Register and Prescription Centre database	These databases are maintained by the Finnish Social Insurance Institution. The Special Reimbursement Register holds information on individuals entitled to special reimbursement for medical expenses. The Prescription Centre database holds information on individuals using selected medications of interest.
Register of Primary Health Care Visits (24)	The register is held by Finnish Institute for Health and Welfare and holds data on all primary health care services delivered in Finland.
Norway	
The Emergency Preparedness Register for Covid-19 (25) (consisting of the data sources below)	Data for the Norwegian analyses were collected through the Emergency preparedness register for Covid-19 ("Beredt C19"), which is administered by the Norwegian Institute of Public Health, according to the Norwegian Health Preparedness Act §2-4. The register was established in 2020 to provide authorities with up-to-date information on prevalence, causal relationships, and consequences of the Covid-19 epidemic in Norway and captures the entire population. The register includes information from the healthcare system and the national health registers presented below.
Norwegian Population Register	The register holds information on birthdate, immigration, emigration status, and death for all residents of Norway.
State register of employers and employees (NAV AA register) (26)	The register holds lists of all employment relationships in Norway for which employers and contractors are obliged to report to. Employees are classified according to the Norwegian Standard Classification of Occupations which we then used to identify whether individuals were health care personnel.
The Norwegian Information System for the Nursing and Care Sector (IPLOS) (27)	The register contains information on the health care services provided by municipalities and reporting of applicants and recipients of such services is mandatory in Norway. Available data includes information on home care services and out-of-hospital institutional care, including nursing home stays.
The Norwegian Immunisation Register (SYSVAK) (28)	The register holds information on administered vaccines in through the Norwegian vaccination programme, including date of administration and type of vaccine/trade name. For the Covid-19 vaccines, reporting to the register is mandatory.

Country/data source	Details
Norwegian Surveillance System for Communicable Diseases (MSIS)	The register holds information on selected infectious diseases for which reporting to the register is mandatory, including all Covid-19 tests and testing date and results.
The Norwegian Patient Registry (NPR) (29)	The register holds data on all contacts with specialist health-care services in Norway, including admission and discharge dates diagnoses recorded according to ICD-10 during hospitalisation or outpatient contact.
The Norwegian Intensive Care and Pandemic Registry (NIPaR) (30)	This is a national clinical registry that was expanded to include Covid-19 patients in conjunction with the Covid-19 pandemic. The register holds information on all patients who have tested positive for SARS-CoV-2 and were admitted to hospital including intensive care unit admissions. It is mandatory for all Norwegian hospitals to report to this register.
Sweden	
The Total Population Register (31)	The register is held by Statistics Sweden and contains data on the unique personal identifier assigned to all individuals in Sweden plus general demographic information such as date of birth, sex, country of birth, place of residence, and date of immigration and emigration.
The Cause of Death Register (32)	The register holds information on date of death and underlying as well as contributing causes of death.
The Longitudinal Integrated Database For Health Insurance And Labour Market Studies (LISA) (33)	The database is held by Statistics Sweden and holds many socioeconomic variables such as data on occupation which we used to identify whether individuals were health care personnel.
Register On Persons In Nursing Homes (34)	The register is held by the National Board of Health and Welfare and holds data on nursing care given in either nursing homes, own homes or other institutions to elderly and/or persons with physical, psychiatric or intellectual disabilities.
The National Vaccination Register (35)	The register is held by the Public Health Agency of Sweden and contains information on administered Covid-19 vaccines in Sweden including data on date of administration, the specific vaccine products, substance, formulation, batch number and dose number (for repeated doses).
Register On Surveillance Of Notifiable Communicable Diseases (Sminet) (36)	The register is held by the Public Health Agency of Sweden and contains information on notifiable diseases (for which reporting is mandatory) reported by either the analysis performing laboratories, the treating physician or autopsy performing physician, in accordance with the Swedish Communicable Diseases Act. Data included are e.g., date of disease occurrence, date of testing, date of positive test, and diagnoses.
The Swedish Patient Register (37,38)	The register is held by the National Board of Health and Welfare and comprises data on all in- and outpatient hospital specialist care in Sweden including data on dates of admission and discharge, whether hospitalisation was planned or acute, codes for discharge diagnoses (recorded according to ICD-10-SE) and surgical procedures, whether discharged as deceased, to own private residence or other health care facilities, and type of department.

# 9.5 Study size (sample size and power)

Based on data from our previous work, we expect to be able to include at least 3.4 million individuals who have received a bivalent or monovalent booster as a fourth Covid-19 vaccine dose across the 4

Nordic countries (1.6 million BA.4-5 booster; 1.0 million BA.1 booster; and 0.9 million ancestral-strain monovalent booster vaccinated).(1) The statistical power of our proposed study is reflected in the VE results from our recent Nordic study on the VE of the bivalent boosters (based on data up until April 2023).(1) Based on these data (with follow-up to day 90 from the fourth dose vaccination date), we expect to be able to include at least 2,250 Covid-19 hospitalised individuals across the four countries who at time of hospitalisation had previously received four vaccine doses. The statistical power, however, will most likely be reduced for some subgroup analysis, also owing to the restricted target trial emulation study design. However, this is a trade-off in the effort of constructing more comparable groups and, thus, better causal inference.

## 9.6 Data management

[figure not shown]
No individual-level data can or will be shared between countries or with EMA. Each country is the sole data owner and controller of their own data. Only country-specific results will be shared and combined results will be generated using meta-analysis. Data management and statistical analyses will be conducted using a Common Data Model (CDM). The analytical group in Denmark will code the statistical analyses using R-scripts (R version 4.2.2.). The R-scripts will be made available on GitHub (also during the programming phase to facilitate input and comments). The analysts in each of the participating countries will then run the R-scripts and return the output to Denmark. The country-specific results will be combined using meta-analysis in Denmark.

## 9.7 Data analysis

#### **Procedures**

[figure not shown]
We will use a matched study design to evaluate the effectiveness of a bivalent BA.1 or BA.4-5 (or monovalent [original]) mRNA-booster vaccine (as the fourth dose) in comparison with having received three monovalent vaccine doses only (i.e., nonboosted with a fourth dose) as well as between fourth dose recipients. For the boosted vs nonboosted (i.e., 4 vs 3 dose) comparisons, individuals who have received a fourth dose will be matched on the day of vaccination with individuals who have not yet received a fourth dose. Individuals will be matched on age (5-year bins), calendar time according to when the third dose was received (monthly bins), and a propensity score including sex, region of residence, vaccination priority groups (i.e., individuals at high-risk of severe Covid-19 or healthcare workers), selected comorbidities (chronic pulmonary disease, cardiovascular conditions or diabetes, autoimmunity-related conditions, cancer, and moderate to severe renal disease), and previous history of SARS-CoV-2 infection characteristics. The day the fourth dose was administered within each matched pair will serve as the index date for both individuals. If individuals who were included as a

matched nonboosted (previously three-dose vaccinated) individual (i.e., a reference individual) received a fourth dose later than the assigned index date, they will be allowed to potentially re-enter as a fourth-dose recipient in a new matched pair on that given date. The figure below illustrates the study cohort construction.

For the between booster (i.e., 4 vs 4 dose) comparison, BA.4-5 booster and BA.1 booster recipients (as a fourth dose) will be matched on age (5-year bins), calendar time according to when the fourth dose was received (monthly bins), and a propensity score including sex, region of residence, vaccination priority groups (i.e., individuals at high-risk of severe Covid-19 or healthcare workers), selected comorbidities (chronic pulmonary disease, cardiovascular conditions or diabetes, autoimmunity-related conditions, cancer, and moderate to severe renal disease), and previous history of SARS-CoV-2

infection. The day the fourth dose was administered will serve as the index date for each respective individual. The figure below illustrates the study cohort construction.

We will follow individuals from day 8 after the index date (to ensure full immunisation among booster recipients) up until the day of an outcome event, 365 days has passed since the index date (i.e., allowing up to 357 days of follow-up since day 8), receipt of additional booster, death, emigration, or end of the study period, whichever occurs first.

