#### 9.3 Variables

#### **Exposures**

The Nordic countries implemented national vaccination campaigns against SARS-CoV-2 from December 27, 2020, providing free vaccinations to all residents. Phased distribution plans were implemented prioritising vaccination of individuals at highest risk of Covid-19 complications (nursing home residents, healthcare workers, and individuals of older age). Denmark and Norway almost exclusively used mRNA vaccines after full or partial discontinuation of AZD1222 in March 2021 due to serious but rare events of thrombosis with thrombocytopenia. The AZD1222 was similarly halted in Finland and Sweden for the younger population but continued as part of the utilized primary course schedules for the population older than 64 years. The mRNA vaccines have been predominantly used in all countries for booster vaccinations. Ad26.COV2.S has seen very limited use. The Nordic countries have vaccinated around 6 times more individuals with BNT162b2 than with mRNA-1273. Prioritized fourth dose vaccination rollouts to the vulnerable elderly and those living in nursing home

facilitieswere initiated in spring 2022 in Finland, Norway and Sweden, and has been offered more broadly to the general population since summer 2022. Fourth dose vaccination in Denmark was initiated in September 2022, coinciding with the time of the authorization of use of the bivalent boosters. Similar to previously received vaccination doses, the fourth vaccine dose has been classified according to vaccine brand and also according to whether it was a bivalent BA.1, bivalent BA.4-5, or monovalent (original) mRNA-booster vaccine.

For objective #3, we will for the 4 vs 3 dose comparison combine BA.1 and BA.4-5 bivalent boosters to increase statistical power. Depending on data availability, we will stratify this analysis by bivalent booster type.

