#### **Covariates**

For our main cohort analysis objective #1-2 and #5-8, we will take the following potential confounders into account: age (using birth cohort), sex, region of residency, calendar time of last mutual vaccine dose (i.e., either third or fourth dose depending on boosted vs unboosted- [i.e., 4 vs 3-] or between boosters- [i.e., 4 vs 4-] analyses), vaccination priority group (nursing home residents, healthcare personnel, at risk of severe Covid-19 due to comorbidities), previous SARS-CoV-2 infection and selected comorbidities. For the Covid-19 hospitalised cohort analysis (objective #3), we will also include length of hospitalisation as a covariate (as a proxy for severity of event) but not use previous SARS-CoV-2 infection history (as per eligibility criteria, all included are SARS-CoV-2 infected [as hospitalised due to this infection] and any previous SARS-CoV-2 infection is most likely not a strong confounder within the comparison). For the immunocompromised cohort analysis (objective #4), we will also include subtype of immunocompromised condition (as categorized in the 6 levels in the table above). In addition, we will assess the data distribution to help find the optimal categorization of the variables "Time since SARS-CoV-2 infection", "Time between primary course and first booster", and "Time between first and second booster". Further details of covariate definitions are provided in table below.

Variable	Country	Data source and details	Values/codes
Ago	Denmark	The Civil Registration System. Recorded birth year. Age defined as the country-specific start date minus birth year.	Categorical (for adjustment, using birth year): 5-year bins
Age	Finland	The Finnish Population Information System. Recorded birth year. Age defined as the country-specific start date minus birth year.	Binary (for stratification): ≥ 70 years</td

Variable	Country	Data source and details	Values/codes	
	Norway	Norwegian Population Register. Recorded birth year. Age defined as the country-specific start date minus birth year.		
Sweden		The Total Population Register. Recorded birth year. Age defined as the country-specific start date minus birth year.		
	Denmark	The Civil Registration System. Defined as registered sex.		
Sex	Finland	The Finnish Population Information System. Defined as registered sex.	Binary: male, female	
Jex	Norway	Norwegian Population Register. Defined as registered sex.	billary. maie, lemaie	

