## Statistical analysis

We will use logistic regression to estimate the propensity score of receiving a specific booster dose given covariates as predictors. We will match (without replacements) on age, calendar time of last mutual vaccine dose (i.e., third or fourth dose), and the propensity score (with a calliper width of 0.01).

Cumulative incidences will be estimated by the Kaplan-Meier estimator, and from these we will calculate the comparative VE as 1 – risk ratio at day 365. The corresponding 95% CI will be calculated using the delta method. Country-specific estimates will be combined by random-effects meta-analyses implemented using the *mixmeta* package in R.

Comparative waning will be estimated using meta-regression.(39) First, we will estimate the VEs (in the specific comparison being evaluated) in each consecutive three-months period (day 8-90, day 91-180, 181-270, and 271-365) by stratification on time since booster vaccination. Second, the resulting estimates will be analysed using meta-regression to provide a ratio of VEs per three-month intervals as a measure of waning.

Subgroup analyses will be conducted according to sex, age groups ( $</\ge70$  years), time since last SARS-CoV-2 infection (<6, 6-12, >12 months), time between primary course and first booster ( $</\ge12$  months), time between first and second booster ( $</\ge12$  months), and bivalent booster brand (Pfizer-BioNTech and Moderna).

*All-cause mortality (objective #3)* 

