#### 9.9 Limitations of the research methods

The study has a number of limitations. First, the observational nature of the study hampers the possibility to fully exclude residual unmeasured confounding. A major concern would be presence of such unmeasured confounding factors that were unevenly distributed between compared matched

groups (i.e., not indirectly adjusted for by the set of included covariates, that is, proxies). We will include a range of pre-specified confounders and study a population representative of the general audience targeted for bivalent booster vaccinations. The precision of our exposure, Covid-19 vaccination, will rely on the registered vaccination within the registers and recorded time of administration. To the best of our knowledge, the assignment of the type of booster as the fourth dose was unselective during the study period (except for the initial prioritisation of older and vulnerable individuals during the first two weeks of study period in Denmark) and our study period should reflect a time of which fourth dose vaccination was offered to the general public.

For the outcomes of Covid-19 hospitalisation and death, our outcome definition will most likely also capture a small proportion of cases where the infection with SARS-CoV-2 only partly contributed to or coincided with the timing of hospitalisation, that is, hospitalisations or deaths where SARS-CoV-2 infection were not the sole cause. In addition, those acquiring SARS-CoV-2 infection (and who were hospitalised or died) without PCR test results we will not capture; we have no information on at-home antigen testing for SARS-CoV-2 infection. PCR testing has been advised as confirmatory to antigen testing and recommended for individuals at risk of severe Covid-19. Any of such outcome misclassification would most likely tend to bring the estimates toward a null effect.

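### Both matched comparisons control age only in 5-year bins and leave it out of the listed propensity score, although birth year is held in every country

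*Protocol*

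**What the plan says.** The 4 vs 3 match is specified in section 9.7 (Procedures): individuals are "matched on age (5-year bins), calendar time according to when the third dose was received (monthly bins), and a propensity score including sex", with region, vaccination priority group, five comorbidity groups and previous infection completing the score. The 4 vs 4 match follows the same pattern: "BA.4-5 booster and BA.1 booster recipients (as a fourth dose) will be matched on age (5-year bins" together with month of fourth dose and a propensity score with essentially the same contents. Age is in neither list.

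The Statistical analysis part of 9.7 describes the model only as the "propensity score of receiving a specific booster dose given covariates as predictors". It then names age, calendar time of the last mutual dose and "the propensity score (with a calliper width of 0.01" on the score as three separate matching items.

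The covariate table in 9.3 gives the same source for age in every country: "Recorded birth year. Age defined as the country-specific start date minus birth year". Its coding for adjustment is "Categorical (for adjustment, using birth year): 5-year bins", plus a binary split at 70 years for stratification.

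VE is one minus the ratio of Kaplan-Meier cumulative incidences in the matched cohort, with no further covariate adjustment.

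**The concern.** The matching is the only age control behind the main VE estimates. Within a 5-year bin nothing is designed to make boosted and comparison members the same age. If the chance of being boosted on a given day changes with age inside a bin, and the risk of hospitalisation or death also changes with age, the matched risk ratio carries the difference. Bias of this kind does not shrink with cohort size.

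The protocol gives some reason to expect a gradient in the 4 vs 3 comparison. Section 9.3 (Exposures) says the phased campaigns put first "nursing home residents, healthcare workers, and individuals of older age". Section 9.9 acknowledges prioritisation of older and vulnerable people in the first two weeks of the Danish study period. The 4 vs 3 design pairs a person boosted on a day with someone not yet boosted on that day, so a roll-out descending by age would tend to make the boosted member the older one.

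The planned diagnostics (9.8) assess matched parameters. If age is checked in the form in which it is matched, the 5-year bin, it will be perfectly balanced by construction and a drift inside the bin will not show.

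**Working it through.** **What the text allows**

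- A 5-year birth-year bin holds five birth years, so two members of a pair can differ by at most 4 birth years.
- The general phrase about covariates as predictors might be read as putting age into the score. With age coded for adjustment in 5-year bins, it would still be no finer than the exact match.
- The stratification at 70 years does not narrow the bins.

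**Size of a possible bias**

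The protocol gives no figure to reproduce, neither a risk gradient by age nor an uptake gradient within a bin. Both are assumptions here.

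- Birth years within a bin: a = 0, 1, 2, 3, 4 (older = higher), equally frequent (assumption).
- Risk ratio per year of age, r: 1.05 to 1.12 (assumption).
- Odds ratio of being boosted per year of age within a bin, g: 1.05 to 1.20 (assumption), with 50% boosted at the middle year.
- Reference VE: 67.8% (section 7, BA.4-5 against hospitalisation), so RR = 1 − 0.678 = 0.322.

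Formulas: odds(a) = g^(a−2) and p(a) = odds/(1 + odds). The weights w1 ∝ p and w0 ∝ 1 − p each sum to 1. The bias factor is B = Σ w1·r^a / Σ w0·r^a, and the VE as read is 1 − 0.322 × B.

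Worked case, r = 1.08 and g = 1.10:

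- p = 0.452, 0.476, 0.500, 0.524, 0.548
- w1 = 0.181, 0.190, 0.200, 0.210, 0.219; w0 is the same list reversed
- mean of a: 2.095 boosted and 1.905 comparison, difference 0.19 years
- r^a = 1, 1.080, 1.166, 1.260, 1.360
- B = 1.1819/1.1648 = 1.015
- VE read = 1 − 0.322 × 1.015 = 67.3%

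Setting the middle-year uptake to 10% or 90% leaves B at 1.015.

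Bias factor, with the value that a VE of 67.8% would show:

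| g per year (mean age difference) | r = 1.05 | r = 1.08 | r = 1.12 |
|---|---|---|---|
| 1.00 (0 years) | 1.000; 67.8% | 1.000; 67.8% | 1.000; 67.8% |
| 1.05 (0.10) | 1.005; 67.6% | 1.008; 67.6% | 1.011; 67.4% |
| 1.10 (0.19) | 1.009; 67.5% | 1.015; 67.3% | 1.022; 67.1% |
| 1.20 (0.36) | 1.018; 67.2% | 1.028; 66.9% | 1.042; 66.5% |
| 1.50 (0.78) | 1.039; 66.6% | 1.061; 65.8% | 1.091; 64.9% |

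The VE column uses unrounded factors. For a contrast whose true RR is 1, the apparent VE is 1 − B, which is −0.5 to −4.2 points over g = 1.05 to 1.20. The last row is a stress case outside the assumed range: g = 1.5 means 1.5^4 = 5.06-fold odds across one bin.

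The signs apply when the boosted are older within bins. If they are younger, VE is biased upwards instead.

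**The case against.** The strongest reply is that the plan contradicts nothing. The covariate table and both parts of 9.7 agree with one another, and 5-year bins already remove most of the age variation. If ages 50 to 94 are taken as uniform, the within-bin variance is 2.0 out of 168.7, or 1.2%. This stands, and it is why the effect in the table is small.

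Second, other design features may carry some age order. The 4 vs 3 match is also exact on month of third dose, and 9.2 excludes people given a fourth dose before the country start dates, which removes many early prioritised recipients. The age prioritisation in 9.3 describes the whole campaign, not uptake within the study cohort. These points weaken the mechanism. They do not balance age within a bin, since two people vaccinated in the same month can still be 4 birth years apart.

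Third, the form of the model and the content of the diagnostics could be left to an analysis plan or the shared R scripts. But the protocol itself fixes the 5-year coding and lists the score's contents, so a script that follows it will not contain single-year age.

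A reader might go further and infer that the BA.4-5 vs BA.1 contrast is the most exposed. The documents do not support that. Section 9.9 describes assignment of booster type as unselective, "except for the initial prioritisation of older and vulnerable individuals during the first two weeks of study period in Denmark", and this contrast is matched on month of fourth dose.

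A reader might also divide the two cited VEs, 0.322/0.342 = 0.94, and argue that an age difference could produce that ratio alone. Those VEs come from separate comparisons against unboosted people, and 9.9 says matched comparisons should primarily be interpreted separately. Section 7 reports the direct comparison as showing no significant difference.

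**Conclusion.** The point holds as an avoidable weakness in confounding control, not as an error or a demonstrated bias. In both matched comparisons age is controlled only to the 5-year bin, finer data are held, and nothing downstream makes up for it.

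Under the assumed gradients the bias factor is about 1.005 to 1.042. That is 0.2 to 1.3 VE points on 67.8%, and 0.5 to 4.2 points on a null contrast. It is zero if booster receipt does not vary with age inside a bin. The range rests entirely on the assumed risk and uptake gradients. The documents supply neither, and they do not rank age against other risk factors.

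The mechanism is most plausible for 4 vs 3. For booster type it is not documented beyond the two-week Danish exception.

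**What to change.** Keep the exact match on 5-year age bins. In the propensity model for both the 4 vs 3 and the 4 vs 4 match, add age derived from birth year as a continuous or spline term, and list it in 9.7 (Procedures) and in the covariate table in 9.3. In the matching diagnostics under 9.8, report the standardised difference of single-year age after matching.

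No new data are needed. The cost is one term in the common R script and one line in the diagnostics, with possibly slightly fewer pairs within the 0.01 calliper where age predicts booster receipt. With at least 3.4 million fourth-dose recipients expected (9.5), a small loss should be affordable. The 5-year bins do not have to be narrowed.
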